10.4 PROTOCOL AMENDMENT HISTORY

Version	Date	Description of Change	Brief Rationale
1.1	2020.12.17	Section 1.3: Moved the timing of the HADS and nutritional assessments from day of discharge to screening/enrollment.	This will streamline the workflow. Coordinators will be present to answer participants' questions and ensure data collection is completed. This will also decrease the amount of activities the participant needs to complete immediately upon discharge.
		Section 8.2 Added the HRQOL and nutritional assessments to the list of items at the screening/baseline visit.	For internal consistency within the protocol to match the change described above. Section 8.2 now matches the schedule of activities.
1.2	2021.04.09	Added language to describe the smartphone inclusion criteria more clearly (bolded text is new): A smartphone with a compatible Apple or Android operating system installed and able to download and use ManageHF including accepting all permissions	To ensure the app works as intended, the smartphone must run a compatible operating system and all permissions must be accepted.
1.2	2021.12.03		The study workflow has been updated to reflect the changes included in this amendment.
1.3	2021.12.03	Screening, recruitment, enrollment, and the baseline	Recruitment and enrollment have been slower than

		visit can now occur up to 7 days post-discharge. The visit windows for weeks 6 & 12 have been extended to +/-10 days.	anticipated. The sites have indicated they are experiencing challenges approaching participants before discharge. It is expected that extending the enrollment and baseline visits to up to 7 days post-discharge will improve enrollment by giving the participants and coordinators additional time to complete all enrollment activities.
		The 1-question NHYA survey is not required for randomization	Due to low survey completion at weeks 6 & 12, we are extending the visit windows to give participants more time to complete the survey and give the coordinators more time to follow up.
		Process for randomizing participants who are rehospitalized has been spelled out.	This one question survey is not a primary outcome measure and we do not want to lose participants due to 1 missing question.
			By allowing enrollment to occur after discharge, there is a higher likelihood a participant could be rehospitalized prior to randomization.
5.1	2021.12.03	Inclusion criterion #1 – removed "and able to provide consent"	This text was redundant as it is already mentioned in inclusion criterion #8.
		Inclusion criterion #2 – changed language to "or discharged from the hospital within the last 7 days with a diagnosis of"	The language added to inclusion criterion #2 allows participants to be enrolled up to 7 days post-discharge.
5.3	2021.12.03	Added: Participants whose	Low sodium intake is a

		sodium intake is less than 1,500 mg per day as measured by the Block Sodium Screener will be considered screen fails. Added: If a participant is randomized during a re- hospitalization they will be considered a screen failure.	contraindication for this study (exclusion criterion #1) due to the dangers associated with too little sodium. Time to readmission is an outcome measure. Participants who are readmitted prior to randomization would confound the primary outcome measure. They will be recorded as screen failures and can be re-evaluated for eligibility based on their new hospitalization.
6.1.2	2021.12.03	Added an abbreviation for adverse events of special interest (AESI).	Abbreviation was added for ease of reading and for consistency with the use of other abbreviations in the document (e.g. SAE).
		Changed timing of randomization from upon discharge to 'after the baseline MLHFQ is completed'	Since participants may be enrolled after discharge, the text was updated to reflect that randomization will occur after the MLHFQ is completed.
		Removed reference to after discharge.	Removed since participants may be enrolled after discharge.
7.2	2021.12.03	Removed: Adverse events of special interest will be collected from the time of discharge through study completion or study withdrawal/discontinuation.	Section 8 details how AESIs will be captured.
7.3	2021.12.03	Revised text: A participant will be considered lost to follow-up if he or she fails to completely engage (i.e. never uses the study devices or interacts with the mobile app does not complete surveys at week 6 and 12)	Study endpoints use data from weeks 6 and 12. If data is missing from both time points, the participant will be considered lost to follow up.

		with the mobile application and is unable to be contacted by the study site staff. Added: "at week 12" to bullet point #3.	If a participant is unreachable at week 6, every attempt should be made to contact the participant at week 12 before considering the participant lost to follow up. A medical chart review will be conducted at week 12 to gather any available
		Added: A medical record review at the 12-week visit will be completed in order to obtain various endpoints.	endpoints.
8.1	2021.12.03	Added a paper copy option for the FFQ.	Due to the length of the FFQ, the sites have indicated some of their participants would prefer to complete the survey via paper instead of electronically.
8.2	2021.12.03	Reordered baseline questionnaires	Administrative change only to reflect the order of the questionnaires as they appear in the real-world
		Indicated that the Block Sodium Screener is a screening assessment	The Block Sodium Screener is used as a screening instrument to rule out participants whose sodium intake is too low and further reduction could cause harm.
		Summary of assessment table – updated time commitment for the FFQ from 35 minutes to 45 minutes.	Based on feedback from the coordinators, the FFQ is taking approximately 45 minutes to complete.
8.3.5	2021.12.03	Revised text (bolded text is added): AESI will be collected from the time of discharge for participants consented inpatient and from time of consent for participants consented outpatient. AESI will be	The clarifying language is necessary to describe the timeframe for collecting AESI based on hospitalization status at time of consent (inpatient vs outpatient).

		collected until a participant completes study participation	
8.3.6	2021.12.03	Revised text (bolded text is added): SAEs and AESI that occur from (1) the time of discharge for those consented inpatient or (2) the time of consent for those consented outpatient through completion of the final study visit will be reported in the ManageHF database in the following manner	The clarifying language is necessary to describe the timeframe for collecting SAEs and AESI based on hospitalization status at time of consent (inpatient vs outpatient).
8.3.7	2021.12.03	Revised text (bolded text is added): SAEs are reportable from the time of discharge or consent (based on hospitalization status) until a subject	The clarifying language is necessary to describe the timeframe for collecting SAEs based on hospitalization status at enrollment (inpatient vs outpatient).
10.1.9.1	2021.12.03	Added text: Due to the length of the FFQ, paper copies may be available for participants who prefer to complete a paper and pencil version.	Due to the length of the FFQ, the sites have indicated some of their participants would prefer to complete the survey via paper instead of electronically.
10.1.3	2021.12.03	activate the devices, the University of Michigan and	Providing Withings with the participant's email address will allow the participant to receive a shipping confirmation email with tracking information.
10.3	2021.12.03	Added: AESI to the abbreviation table.	Added for internal consistency of the document.
1.2, 5.1, 5.2	2022.04.18	Update inclusion and exclusion criteria	Due to lower than expected recruitment, the inclusion and exclusion criteria have been revised to include a broader pool of patients with heart failure.
5.4	2022.04.18	Added compensation with timing and dollar amount.	Participant incentives have been added to improve

	Added texting as a participant contact method.	participant recruitment and retention The DSMB recommended adding texting as participant contact method to improve participant retention.

CMP	Clinical Monitoring Plan
COC	Certificate of Confidentiality
CONSORT	Consolidated Standards of Reporting Trials
CRF	Case Report Form
DCC	Data Coordinating Center
DHHS	Department of Health and Human Services
OSMB	Observational Study Monitoring Board
DRE	Disease-Related Event
EC	Ethics Committee
eCRF	Electronic Case Report Forms
FDA	Food and Drug Administration
FDAAA	Food and Drug Administration Amendments Act of 2007
FFR	Federal Financial Report
GCP	Good Clinical Practice
GLP	Good Laboratory Practices
GMP	Good Manufacturing Practices
GWAS	Genome-Wide Association Studies
HIPAA	Health Insurance Portability and Accountability Act
IB	Investigator's Brochure
ICH	International Conference on Harmonisation
ICMJE	International Committee of Medical Journal Editors
IDE	Investigational Device Exemption
IND	Investigational New Drug Application
IRB	Institutional Review Board
ISM	Independent Safety Monitor
ISO	International Organization for Standardization
ITT	Intention-To-Treat
LSMEANS	Least-squares Means
MedDRA	Medical Dictionary for Regulatory Activities
MOP	Manual of Procedures
MSDS	Material Safety Data Sheet
NCT	National Clinical Trial
NIH	National Institutes of Health
NIH IC	NIH Institute or Center
OHRP	Office for Human Research Protections
PI	Principal Investigator
QA	Quality Assurance
QC	Quality Control
SAE	Serious Adverse Event
SAP	Statistical Analysis Plan
SMC	Safety Monitoring Committee
SOA	Schedule of Activities
SOC	System Organ Class
SOP	Standard Operating Procedure
UP	Unanticipated Problem
US	United States

4 Introduction

4.1 Preface

This statistical analysis plan (SAP) describes the statistical methods and analyses for the ManageHF study. This document should be read in tandem with the ManageHF protocol version 3.1, dated September 27, 2022.

The Manage HF study (NCT04755816) is a multicenter 12-week randomized controlled double-blind 2x2 factorial clinical trial. This study will investigate the effectiveness of two contextual just-in-time adaptive interventions (JITAs) delivered via a mobile app for heart failure patients. The clinical worsening intervention targets self-management of behaviors to prevent worsening of a patient's heart failure symptoms. The dietary sodium intervention promotes lower sodium intake. Eligible participants will be randomized to the dietary sodium intervention, the clinical worsening intervention, both interventions, or no intervention in a 1:1:1:1 manner, stratified by site, gender, and HF type (HFpEF versus HFrEF).

4.2 Scope of the analyses

The purpose of this document is to describe the statistical analyses to be conducted to meet the primary and secondary objectives of the ManageHF study. Ancillary analyses are not covered in this document.

5 Study Objectives and Endpoints

5.1 Study Objectives

5.1.1 Primary Objectives

To determine the impact of two unique adaptive mobile application interventions on death, HF readmissions, and health-related quality of life (HRQOL) in HF patients.

5.1.2 Secondary Objectives

Examine the effect of the two interventions on the individual components of the primary composite endpoint and relative change in heart failure symptoms.

5.2 Endpoints

5.2.1 Primary Endpoint

1. The hierarchical composite of time to death from any cause, time to first HF readmission, and change from baseline to week 12 in quality of life as measured by the Minnesota Living with Heart Failure Questionnaire (MLHFQ).

5.2.2 Secondary Endpoints Endpoint

1. Time to all-cause mortality
2. Time to first HF readmission
3. Change in MLHFQ over 12 weeks

6 Study Methods

[figure not shown]
6.1 General Study Design and Plan

This phase III trial will determine the effectiveness of two interventions within a mobile application and builds on the research team's previous work. The two mobile interventions are the clinical worsening intervention and the sodium intake intervention. Our central hypothesis is that a patient-centered mobile application with contextual just-in-time adaptive interventions (JITAs) about self-management during a clinical worsening and dietary sodium will improve the health status of HF patients.

This study is a 12-week prospective randomized controlled double-blind 2x2 trial. See section 1.2 for an overview of the schema. The 2x2 factorial arms of the study are: 1) Both the sodium intervention and the clinical worsening intervention, 2) the sodium intervention only, 3) the clinical worsening intervention only, and 4) no intervention. Eligible participants will be randomized to the dietary sodium intervention, the clinical worsening intervention, both interventions, or no intervention in a 1:1:1:1 manner, stratified by site, gender, and HF type (HFpEF versus HFrEF). The DCC unblinded statistician will prepare the randomization schedule, using computer-generated block randomization with the random block size(s) known only by the DCC. See Section 9.3.2 for more stratification details.

This multicenter clinical trial will be managed by the University of Michigan through the clinical coordinating center (CCC) and the

data coordinating center. The CCC will be led by chief principal investigator, [name], and the data coordinating center will be led by the Statistical Analysis of Biomedical and Educational Research (SABER) unit. Nine sites, including the lead site, have been selected because of their extensive experience either in the NHLBI Heart Failure Research Network or completion of several randomized clinical trials at the site.

6.2 Inclusion-Exclusion Criteria and General Study Population

All eligibility criteria must be met in order to participate in this study:

1. Age 18 years and older at screening
2. Currently admitted or discharged from the hospital within the last 14 days with a diagnosis of acute or acute on chronic decompensated HF.
3. Based on one of the EF criteria (LVEF within 12 months of randomization. BNP or NT-proBNP criteria within 30 days prior to randomization):
 - Left ventricular ejection fraction (LVEF) $\leq 40\%$.
 - LVEF $>40\%$ and BNP $> 175 \text{ pg/ml}$ or NT-proBNP $> 700 \text{ pg/ml}$. Thresholds for NT-proBNP and BNP for LVEF $> 40\%$ will be corrected for body mass index (BMI) using a 4% reduction per BMI unit over 25 kg/m^2 .*
4. Have a personal physician for follow-up
5. A smartphone with a compatible Apple or Android operating system installed and able to download and use ManageHF including accepting all permissions
6. A valid email address
7. Fluent in spoken and written English
8. Signed written informed consent. (Note that each participant must be able to consent for themselves.)

*BNP threshold for eligibility:

BMI	BNP LVEF >40	NT- ProBNP LVEF >40
25	175	700
26	168	672
27	161	644
28	154	616
29	147	588
30	140	560
31	133	532
32	126	504
33	119	476
34	112	448
35	105	420
36	98	392
37	91	364
38	84	336
39	77	308
40	70	280
41	63	252
42	56	224
43	49	196
44	42	168
45	35	140
46	28	112
47	21	84
48	14	56
49	7	28

An individual who meets any of the following criteria will be excluded from participation in this study:

1. Contraindication to recommending a sodium restriction diet
2. Scheduled intervention for primary valvular heart disease will occur during the study period
3. Cardiac resynchronization therapy (CRT) within 3 months prior to screening or current plan to implant CRT device during the study period.
4. Dialysis
5. Previous cardiac transplantation or implantation of a ventricular assistance device or similar device.
6. Listed status 1, 2 or 3 for heart transplant
7. Implantation of a ventricular assistance device is expected within 3 months after randomization
8. Non-cardiac illness with expected survival of less than 3 months
9. Discharge to a setting other than home
10. Requirement for chronic inotropic therapy (e.g. milrinone, dobutamine)
11. Inability to use Withings devices due to equipment limitations or contraindications
12. Currently pregnant or intend to become pregnant during the study period.

6.3 Randomization and Blinding for Bias Reduction

Participants were randomized after all screening assessments have been completed and the investigator has verified that eligibility criteria have been met. At the time of randomization, participants were assigned a unique randomization number. Eligible participants were randomized to the dietary sodium intervention, the clinical worsening intervention, both interventions, or standard care in a 1:1:1:1 manner, stratified by site, gender, and HF type (HFpEF versus HFrEF). The DCC unblinded statistician prepared the randomization schedule, using computer-generated permuted block randomization with the random block size(s) known only by the DCC. The randomization schedule was provided to software developers who built the mobile apps. Participants who withdraw from the study prior to completion of the treatment period will not be replaced.

This study is double-blinded, with participants, investigators, and study team masked to study assignments. Due to the interventions using push notifications, users will likely be able to guess which intervention group they are in over time. That is the nature of this type of research. Implications of this are unknown given the objective nature of our primary composite endpoint. Some users could report better HRQOL because they are receiving more push notifications. At the week 12 visit, participants will be asked to complete a short exit questionnaire via Redcap asking them to guess their treatment group.

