6 STUDY INTERVENTION

6.1 STUDY INTERVENTION(S) ADMINISTRATION

6.1.1 STUDY INTERVENTION DESCRIPTION

The mobile application, developed at the University of Michigan, includes two JITAIs that are turned on or off based on the randomization assignment for the clinical trial. The clinical worsening intervention promotes self-monitoring and self-management with a health status indicator that is linked to adaptive, personalized and contextual push notifications to promote a behavioral change (see figure 2). The dietary sodium intervention facilitates lower sodium choices at home, restaurants, and grocery stores using tailored and contextual push notifications.

Both JITAIs use NumberEight, an internet-based service, that use sensors (Wi-Fi, Bluetooth, accelerometer, gyroscope, magnetometer, GPS) on the participant's device to predict their location. User's identifying information is anonymized in NumberEight. The mobile sensor data and NumberEight profiles are not attached to the personalized identifiers (e.g. phone number, email). Data are stored as long as the user is using NumberEight. Study staff will not have access to participants' location during the study period.

Clinical worsening intervention: The intervention adapts to the participant's reported symptoms and provides feedback with a global health status indicator (HSI). The mobile application includes 8 questions which are completed by all (see table 1). After the questions are answered, participants

randomized to the clinical worsening intervention arm will be shown the HSI screen. Access to the HSI screen is restricted to participants in the clinical worsening intervention arms. The HSI screen presents a graphic (figure 2). The HIS graphic is a speedometer-like pictograph that goes from green (good health status) to yellow (fair health status) to red (poor health status). The movement from green to yellow to red is based on the answers to each daily questionnaire. The health status indicator includes text explaining the green, yellow or red status and what they can do for self-management. Additionally, users will receive two push notifications per day in the yellow and three push notifications per day in the red until they are back in the green. The notifications will link to in-app educational content, if appropriate for the notification.

Question score	0	1	2	3	4
Sense of fullness during a meal earlier than usual	Never	Rarely	Sometimes	Most of the time	Always

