8.3 Primary Endpoint Definition

The primary outcome is a hierarchical composite of time to all-cause death, time to first HF readmission, and change from baseline to week 12 in MLHFQ using the win ratio.

Death (from any cause) occurring during the study period will be reported by each site. We do not expect an intervention effect on death but are including the event because of its importance using this methodology.

Readmission is defined as admission to an inpatient unit or stay in an emergency department following discharge after the index hospitalization that results in at least a 24-hour stay.³⁰ Only admissions associated with events that occur on an emergency or unplanned basis will be considered as potential endpoints and then adjudicated. A HF readmission must have clinical manifestation of new dyspnea, orthopnea, paroxysmal nocturnal dyspnea, edema, pulmonary basilar rales/crackles, jugular venous distension, renal hypoperfusion with no other apparent cause or radiological evidence of acute HF and additional increased treatment with either intravenous HF medications (diuretics, inotropes, vasodilators) or mechanical or surgical intervention specifically directed at the treatment of HF. Only readmissions during the study period will be assessed.

The MLHFQ tool consists of 21 questions regarding patients' perception of the effects of HF on their daily lives.²⁹ The questions produce a total score of 0 to 105, with a higher score indicating poorer HRQOL. The MLHFQ will be collected at baseline, 6 and 12 weeks. A score change of 5 or more is considered a clinically significant difference for the hierarchical composite endpoint.

Following the unmatched pairs win ratio method of Finkelstein and Schoenfeld,³⁴⁻³⁶ each participant receiving intervention will be compared to each participant not receiving intervention, resulting in $N_i \times N_{ni}$ pairwise comparisons, where N_i is the sample size for the intervention arm, and N_{ni} is the sample size for the non-intervention arm. For each comparison, "winners" will be determined according to the table below, starting with scenario 1.

Scenario	Time to all-cause death	Time to HF readmission	Change in MLHFQ	Win/loss
1	Low			Loss
	High			Win
2	Tie or both alive	Low		Loss
		High		Win
3	Tie or both alive	Tie or both not hospitalized	Comparator	Loss
			12-week change ≥ 5 points better than comparator	Win
4	Tie or both alive	Tie or both not hospitalized	Comparator	Tied

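### The primary composite is called objective, but roughly half of its decided pairs would rest on self-reported MLHFQ, and no planned output shows how much of the win ratio comes from that tier

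*SAP*

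**What the plan says.** SAP 6.3 and Protocol 6.3 describe the trial as double-blind. They then say that, because the interventions work through push notifications, "users will likely be able to guess which intervention group they are in over time". Three further statements follow:

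- The consequence: "Implications of this are unknown given the objective nature of our primary composite endpoint".
- The concession, in the next sentence: "Some users could report better HRQOL because they are receiving more push notifications".
- The data collection: at week 12, "participants will be asked to complete a short exit questionnaire via Redcap asking them to guess their treatment group".

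SAP 8.3 defines the composite as time to death, then time to first HF readmission, then 12-week change in MLHFQ with a 5-point margin. On the last tier it says: "The MLHFQ tool consists of 21 questions regarding patients' perception of the effects of HF on their daily lives". The same section expects no intervention effect on death.

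SAP 10.2 plans one win ratio with a bootstrap interval and one rank sum test per intervention. SAP 10.3 plans separate secondary analyses: Cox models and Kaplan-Meier curves for death and for first HF readmission, and linear regression for MLHFQ change. SAP 12 defines no other analyses.

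**The concern.** Death is objective, and HF readmission is adjudicated against stated criteria. A 21-item perception score is neither. Group membership is also easy to infer by design. In Protocol 6.1.1, "Access to the HSI screen is restricted to participants in the clinical worsening intervention arms", and users with a yellow or red status receive two or three notifications a day.

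This would matter little if MLHFQ were a rare tie-breaker. It is not: most pairs have no death and many have no readmission, and the plan expects no effect on death. Any signal must therefore come from readmission and MLHFQ. Both primary hypotheses (SAP 10.1) name deaths, HF readmissions and quality of life together. A significant win ratio carried by the MLHFQ tier could then be cited as evidence on all three. The planned output would not let a reader see which tier produced the wins.

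**Working it through.** **The plan's own figures.** The documents state no tier shares, so there is none to reproduce. The planned size is 500 × 0.9 / 2 = 225 completers per arm. A win ratio of 1.30 means 1.30/2.30 = 56.5% winners (printed as 56.6%). The stated 80% power reproduces at 79.2–80.0% with a binomial formula on 450 completers. Whether that formula suits the planned test is a separate question. Only the 225 per arm is used below.

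**Inputs**

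- HF readmission risk h: 19.3% to 26.2%, the two arms of the pilot in Protocol 2.2. That sentence gives the App arm the higher rate yet describes the result as favouring the App, so the figures serve only as a range.
- 12-week death risk d: 0 to 8.9%. The upper end takes one-third dying in a year (Protocol 2.1) at constant hazard: 1 − (2/3)^(12/52) = 8.9%.
- SD of MLHFQ change: Protocol 2.2 gives 55.7 to 42.6, N = 24, p = 0.0078. Assuming a paired t-test, t on 23 df = 2.915, SE = 13.1/2.915 = 4.49, and SD = 4.49 × √24 = 22.0.
- Assumed: equal arms, independent tiers, complete MLHFQ.

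**Share of decided pairs settled by MLHFQ**

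- By death: 1 − (1−d)²
- By readmission: (1−d)²[1 − (1−h)²]
- By MLHFQ: (1−d)²(1−h)² × P(|N(0, 22√2)| ≥ 5), where the last factor is 0.872

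| d | h | Death | Readmission | MLHFQ | Tied | MLHFQ share of decided |
|---|---|---|---|---|---|---|
| 0 | 19.3% | 0 | 0.349 | 0.568 | 0.083 | 62% |
| 0 | 26.2% | 0 | 0.455 | 0.475 | 0.070 | 51% |
| 8.9% | 19.3% | 0.171 | 0.289 | 0.471 | 0.069 | 51% |
| 8.9% | 26.2% | 0.171 | 0.378 | 0.394 | 0.058 | 42% |

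Varying the SD from 15 to 25 widens this to 40–62%. Also letting h run from 11% to 27% (the 30-day rates in the meals pilot) gives 39–77%.

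**A pure reporting shift with no true effect.** For a shift of δ points in the intervention arm only, a tier-3 pair is won with probability 1 − Φ((5−δ)/31.1) and lost with probability Φ((−5−δ)/31.1). At δ = 5 these are 0.500 and 0.374, a tier-3 win ratio of 1.34. Pairs decided by events split evenly.

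- d = 0, h = 19.3%: 0.651 of pairs reach tier 3, so the win ratio is (0.174 + 0.326)/(0.174 + 0.244) = 1.20.
- d = 8.9%, h = 26.2%: 0.452 of pairs reach tier 3, so it is (0.274 + 0.226)/(0.274 + 0.169) = 1.13.

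**Rejection at 225 per arm**, simulating the Finkelstein-Schoenfeld test with SD 22:

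| d, h | 3-point shift | 5-point shift |
|---|---|---|
| 5%, 20% | WR 1.09, 11% | WR 1.17, 26% |
| 8.9%, 26.2% | WR 1.08, 10% | WR 1.13, 19% |

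Repeat runs over d = 5–9% and h = 20–26% span about 9–27%. With no shift, rejection is about 5%. A win ratio on tiers 1 and 2 only stays at about 5% (3.5–6.5%). With no deaths and h = 19.3%, a large-sample approximation, using log-win-ratio variance 4(1+t)/(3k(1−k)(1−t)N) with tie proportion t, k = 0.5 and N = 450, gives 15% at 3 points and 33% at 5.

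**Dilution by the factorial design.** For each main effect, half the comparators receive the other intervention. If any notifications cause the shift, the net contrast is about halved. Simulated over d = 5–9% and h = 20–26%, the win ratio is 1.04–1.09 and rejection about 5–10%.

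**The case against.** Much of the defence of the plan stands.

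- **Event-only results are planned.** A reader might infer from SAP 10.2 that nothing separates events from MLHFQ. SAP 10.3 contradicts that, with hazard ratios and intervals for death and for first HF readmission and a separate MLHFQ model. But those models drop the hierarchy, the pairing and the 5-point margin, so they cannot show how many of the wins came from MLHFQ.
- **The plan does not hide the bias.** It calls the implications unknown and discloses possible HRQOL over-reporting. Every arm receives the app, devices and daily questionnaire (Protocol 4.2).
- **The hypotheses include quality of life.** A reader might infer that a significant win ratio would necessarily be presented as fewer deaths and readmissions. SAP 10.1 also names HRQOL, and component results would appear alongside, so that misreading is possible but not built in.
- **The shift is assumed.** Nothing in the documents supplies 3–5 points; it is chosen as no larger than the plan's own 5-point margin. Participants receiving both interventions are capped at three messages a day (Protocol 6.1.2), which supports the diluted figures. A bias specific to one intervention, such as seeing the HSI screen, would be diluted less.
- **The planned size was not reached.** SAP 8.1 and 14 record early termination for insufficient enrolment. At an assumed 60–100 per arm, a 5-point shift rejects 8–15%, or 6–7% if diluted.
- **A separate outputs file exists.** SAP 17 refers to a tables and listings document that is not available here. Tier counts could be in it, although SAP 12 defines no further analyses.

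**Conclusion.** The point holds in a limited form. Calling the whole composite objective is wrong for its third tier, and that tier would settle roughly 42–62% of decided pairs under the stated assumptions. Missing MLHFQ scores would lower that share. No planned analysis attributes the win ratio to its tiers, no win ratio on death and readmission alone is planned, and the arm guess is collected without a stated use.

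The possible inflation is moderate and depends on assumptions: about 9–27% false rejection if the shift affects only the intervention arm, and about 5–10% if half the comparators share it, both at 225 per arm with 5–9% mortality. These rates do not describe the trial as it ended, but the question of what a win ratio shows remains at any size. The documents do not show that reporting bias occurred. This is an inexpensive improvement to reporting and interpretation and does not invalidate the primary analysis.

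**What to change.** 1. In SAP 6.3 and Protocol 6.3, replace the description of the composite as objective with a statement that death and HF readmission are objective and MLHFQ is self-reported.
2. In SAP 10.2, for each intervention, report wins, losses and ties by tier.
3. In SAP 10.2, add a supportive sensitivity win ratio on tiers 1 and 2 only, with its 95% confidence interval.
4. Tabulate the exit-questionnaire guess by randomized arm.
5. Base any statement about death or readmission on the event-only estimates and their confidence intervals, not on the full win ratio. Requiring only that the event-only estimate point the same way is not enough: in simulation, about 87–100% of false-positive results favouring the intervention would pass, because both statistics share the same chance imbalance in events.

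The cost is one more run of code the plan already needs and two short tables, using data already due to be collected. The event-only win ratio has lower power and can only be supportive.
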